### Procedures

Participants will be recruited through postings on campus and nearby workplaces, pamphlets to Penn Medicine practices, internet advertisements, and local media appearances. Participants will complete an initial phone screen to determine eligibility and assess availability. Participant responses will be reviewed by the principle investigator and if they appear to be eligible, a screening visit will be scheduled. Study staff will complete a clinical interview assessing typical eating and sleep patterns, weight history, and psychiatric status. Participants will also be asked to complete several self-report questionnaires to assess mood, exercise, sleeping and eating patterns, and to examine psychological constructs related to eating and food. Participants will undergo a medical history and physical, and their weight, height, and waist circumference will be measured. Blood pressure, pulse, fasting blood work (which includes tests for a metabolic panel, fasting glucose, HbA1c, lipid panel, and CBC test), and an EKG will also be performed to exclude diabetes, MetS, and other metabolic or cardiac issues. Participants will receive logs to record food, physical activity, and sleep-wake cycles, as used in our previous studies of NES (135,136) and our R21 study, and an actigraph to wear for 10d. Upon completion, study staff will review their logs and actigraphs, and if they meet inclusion criteria, they will be scheduled to undergo the inpatient baseline assessment. After baseline assessment, participants will be randomized to begin the study with either the daytime or delayed eating condition, and they will receive their first 3d of food. The participants will also receive food, sleep, and exercise logs and actigraphs, which they will use for the study duration. Assessment Overview. Assessments will be conducted at 4 phases: 1) pre-eating condition 1; 2) post-eating condition 1; 3) pre-eating condition 2; and 4) post-eating condition 2 (Table 2). Each assessment will include 28h at the Center for Human Phenomic Science (CHPS) where participants will eat according to a standardized schedule. Participants will observe an overnight fast and arrive at CHPS at 0700h. Weight, height, waist circumference, and blood pressure will be measured. Participants will be asked to complete a series of questionnaires to assess psychological measures related to eating and food. Blood will be drawn at 4h intervals for 24h (0800h, 1200h, 1600h, 2000h, 2400h, 0400h and 0800h) to measure circadian rhythms of leptin, ghrelin, melatonin, cortisol and glucose, and of gene expression (43,90,92,95,98,137). A one-time blood sample will also be drawn for genomic analysis. Fasting levels of glucose, insulin, adiponectin, cholesterol, triglycerides, non-esterified fatty acids (NEFAs) and CRP will be measured at 0800h. At the same 4h intervals (0800h, 1200h, 1600h, 2000h, 2400h, 0400h and 0800h), a saliva sample will be obtained using salivette salivary swabs to collect information on changes to the salivary microbiome. This involves participants placing a cotton swab called a Salivette in their mouth to absorb saliva and placing it back into a small tube to be stored; they will be asked to refrain from using toothpaste, mouthwash, or gum beginning at 11 pm the night before admission for this test. After the initial fasting blood draw at 0800h, indirect calorimetry will assess REE and fuel oxidation (RQ) at 0900h. A standardized breakfast will then be served. Next, body composition will be measured using Dual Energy X-ray Absorptiometer (DEXA). At 1200h, blood will be drawn followed by lunch and harvesting of AT at 1300h. Following the AT procedure, participants will complete three computer-based cognitive tests administered by research staff. An afternoon snack, dinner, and evening snack will be served; the last snack will be consumed by 2100h. Participants will then fast overnight in preparation for the FSIGT, and blood draws will continue every 4h. At 0800h, the FSIGT will occur, followed by breakfast, and then discharge from the CHPS. [name], will be contacted in case of medical emergency. In his absence, we will call the hospital operator at [contact] and ask to speak to the endocrinology fellow on call. Dietary Plan and Food Distribution. Research staff will deliver meals and snacks from the CHPS metabolic kitchen 2x/wk, pick up uneaten food, and collect and provide new actigraphs. Participants may also choose to pick up food themselves from the metabolic kitchen if they prefer. Menus will accompany the meals, and participants will check off each food item they consume and note any modifications to their meals and snacks. The CHPS staff will provide portion size training at baseline. Participants will purchase their own beverages and record them on their menus. Mean beverage intake, as reported at baseline, will be factored into each participants total

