
exclusion criteria at the screening visit. We will interview participants using a 24-h food and sleep recall and an abridged Night Eating Syndrome History and Inventory (NESHI; 138) to assess typical eating patterns. Participants will complete the Patient Health Questionnaire (PHQ-9; 133), a 9-item well-validated questionnaire that assesses degree of depressed mood. Persons with scores 9 (minor depressive symptoms) will be excluded. The MINI (134) will assess psychiatric diagnoses. The Morningness-Eveningness Questionnaire (MEQ; 139) will be used to screen out extreme morning and evening chronotypes who would find it difficult to adhere to the sleep or eating schedules. The Pittsburgh Sleep Quality Index (PSQI; 140) measures several sleep domains; the global score for overall sleep quality distinguishes good (5) and poor sleepers (5). The Epworth Sleepiness Scale (ESS; 141) assesses daytime sleepiness; a score 10 is suggestive of sleep apnea, narcolepsy, and idiopathic hypersomnia. The Multivariable Apnea Risk Index (MAP Index; 142) is used to screen out subjects with sleep apnea risk (scores .5). We will use the MAP, PSQI, and ESS to exclude individuals with sleep disorders. If a sleep partner is available, we will also ask him/her to complete a MAP for the participant. We have successfully utilized these screening procedures in our R21 study. In addition to these questionnaires given, participants will also complete 3 other questionnaires at their screening visit to assess food related attitudes. The Behavioral Inhibition System/Behavioral Activation System (BIS/BAS) Scale is a 24-item scale that assesses the sensitivity of systems that react to punishment (BIS) and reward (BAS) cues to better assess an underlying reward sensitivity dimension. The Sensitivity to Punishment (SP)/Sensitivity to Reward (SR) Questionnaire (SPSRQ) is a yes-no response item questionnaire that assesses individual differences in anxiety or sensitivity to the punishment dimension and impulsivity or sensitivity to reward dimension. Lastly, the Barratt Impulsiveness Scale (BIS) assesses common impulsive behaviors and preferences and impulsive personality traits. Once per assessment visit the following self-report questionnaires will be administered: 1. Food Craving Inventory - a self-report measure of general and specific food cravings; 2. Modified Yale Food Addiction Scale (mYFAS), is a 13-item scale identifying those who are most likely to be exhibiting markers of substance dependence with the consumption of high fat/high sugar foods and impairment or distress from eating 3. Temporal Experience of Pleasure Scale (TEPS) - an 18-item self-report measure assessing anticipatory and consummatory facets of pleasure 4. Distress Tolerance Scale (DTS) - measures an individuals (1) ability to tolerate emotions (tolerance); (2) assessment of the emotional situation as acceptable (appraisal); (3) level of attention absorbed by the negative emotion and relevant interference with functioning (absorption); and (4) ability to regulate emotion (regulation) 5. The Eating Inventory (EI) - measures cognitive restraint of eating, disinhibition, and hunger 6. The Power of Food Scale (PFS) - measure of individual differences in appetite-related thoughts, feelings and motivations in environments where plentiful palatable foods are constantly available. 7. The Weight Efficacy Lifestyle Questionnaire (WEL) - a 20-item questionnaire assesses the ability to resist eating in response to certain environmental situations or emotional states. It evaluates self-efficacy in five contexts: negative emotions, food availability, social pressure, physical discomfort, and positive activities. 8. Quality of Life, Enjoyment, and Satisfaction Questionnaire (QLES-Q) - measures domains associated with quality of life factors. It contains 14 items scored on a 0-5 scale with a possible range of 0-70. Lastly, before and after each meal and snack during the assessment visits, participants will be asked to complete a Visual Analogue Scale (VAS) questionnaire to assess hunger, cravings, and fullness. History and Physical. Participants will undergo a history and physical at the outpatient CHPS facility with a nurse practitioner. They will have initial labs drawn, including a metabolic panel (including fasting glucose), lipid panel, CBC, and HbA1c. The nurse practitioner will also complete an EKG (using a GE Mac 5500 HD EKG Machine) and assess blood pressure and pulse (using a Datascope Accutorr V Vital Signs Monitor) in duplicate at 1-min intervals, after a 5-min seated rest. Weight will be measured in light clothing without shoes on a digital scale (Scale-Tronix), and height will be measured on a wall-mounted stadiometer (ProDoc/Detec). Waist circumference will be measured with a flexible tension-controlled measuring tape held at the midpoint between the iliac crest and lowest rib to the nearest 0.1 cm. MetS will be defined by the presence of 3 of the following: abdominal obesity (35 waist circumference for women/ 40 for men); elevated triglycerides (150 mg/dL and/or use of medication for dyslipidemia); low HDL cholesterol (50 mg/dL for women/40 mg/dL for men); elevated blood pressure (130/85 mm Hg and/or hypertensive medications); and elevated fasting blood glucose (100 mg/dL and/or medications to treat pre-diabetic blood glucose levels)(143). A pregnancy test will be given to women at this screening visit, with the exception of post-menopausal women and women who have had surgeries or treatments, such as a hysterectomy, that make them infertile. A urine drug test will be given as well. Outpatient Assessments Food, Sleep, and Activity Logs. Participants will complete a log at baseline, an approach we have used in our R21 and previous studies (41,103,135,136), to track their typical eating, sleep, and physical activity patterns. The food log will be analyzed for caloric and macronutrient content using the NDSR by a CHPS research dietitian. Self-reported sleep and physical activity will be compared to

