
actigraphy data to assess sleep-wake onset and offset and minutes of deliberate physical activity. After baseline, the food log will be a menu based on the foods provided to participants along with the sleep and activity questions. Actigraphy. Wrist actigraphs with light sensors (Spectrum Pro, Philips Respironics Healthcare) will be worn continuously on the non-dominant wrist for the study duration (except when bathing). Actigraphy provides an objective, reliable and valid method for assessing circadian activity patterns, sleep-wake cycles, and light levels in free-living populations with minimal restriction on normal routines (115). Sleep onset, offset, duration, number of nighttime awakenings, and exercise bouts will be determined by actigraphy and confirmed by logs. Inpatient Assessments At each assessment, we will measure weight (kg), height (cm), blood pressure, and waist circumference (see section C.4b.). Participants will also be given a urine drug test and pregnancy test (with the exception of post-menopausal women and women who have had surgeries or treatments, such as a hysterectomy, that make them infertile). Intravenous Placement & Blood Draws for Hormones. Participants will arrive at 0700h at the CHPS and be housed in a 20 lux room (to avoid suppression of melatonin secretion). They will be placed in a supine position and an indwelling intravenous catheter will be inserted at 0730h. Blood draws of 10 ml for hormones will occur every 4h at 0800h, 1200h, 1600h, 2000h, 2400h, 0400h and 0800h. This sampling interval schedule strikes a balance between allowing for detection of circadian phase and amplitude of leptin, ghrelin, melatonin, cortisol and glucose, relative to food intake and sleep, as we and others have documented with circadian cosinor analyses (43,137). Cholesterol, triglycerides, glucose, insulin, adiponectin, NEFAs and CRP will also be measured from the initial fasting blood draw at 0800h on the first morning. No eating will be allowed after 2300h the night before and the night of the assessment. For hormones, blood will be collected in pre-cooled vacutainer tubes containing EDTA and kept on ice until centrifugation at 4°C and then stored at -80°C. Serum will be pipetted into tubes before freezing. Assays will be performed in duplicate by the Penn Diabetes Research Center Radioimmunoassay & Biomarkers Core. Blood Draws for Transcriptomics. 2.5ml whole blood samples also will be collected every 4h at 0800h, 1200h, 1600h, 2000h, 2400h, 0400h and 0800h, into PAXgene Blood RNA tubes (PreAnalytix). This sampling interval schedule allows for detection of the amplitude and circadian phase of gene expression, as has been documented with circadian cosinor analyses (90,98). The PAXgene tubes contain a reagent that helps lyse blood cells to release total RNA and stabilizes the in vivo gene transcription profile by preventing in vitro RNA degradation in blood. The blood will be mixed with this reagent by gently inverting the tube 8-10 times and then will be kept upright at room temperature (18°C to 25°C) for a minimum of 2h and a maximum of 72h. Next, the tubes will be transferred to a -20°C freezer for 24h, and then to an -80°C freezer for storage. An additional 10mL of blood will be collected during the first assessment visit and saved and stored as whole blood. This sample will later be analyzed for the entire genome to provide the researchers with more complete information as to how all genes may contribute to metabolism, sleep and circadian (24-hour) rhythms, an important area of interest to our research. Energy Expenditure. After completion of the first blood draw, participants will remain in bed in a fasted state. At 0900h, resting metabolic rate will be assessed by indirect calorimetry (Parvo Medics TrueOne 2400, Sandy, UT). The Parvo Medics metabolic monitor is an integrated metabolic measurement system which contains O2 and CO2 analyzers, a device for measuring ventilation rates, a gas sampling system, and a computer interface that processes raw data. Resting energy expenditure will be assessed continuously by measuring the volume and the O2 and CO2 concentrations of expired air samples, and will be calculated based on the average VO2 and RQ measures which can be converted to energetic equivalents (kcal/day) (144). Dual Energy X-ray Absorptiometer (DEXA). Following the metabolic testing and breakfast, DEXA (Hologic Discovery Wi Bone Densitometer) will be used to measure total body fat, trunk fat and lean mass (145). AT Biopsies. Using a standard CHPS protocol, subcutaneous white AT will be collected at 1400h by core needle aspiration through a 4-mm gluteal incision and will be treated with RNA Later (Qiagen), snap frozen and stored at -80°C for subsequent RNA extraction (121,122,146,147). Cognitive Inhibition Test Battery. We will use a computer-based battery of tests to assess three aspects of inhibition that have been linked with overeating and disordered eating behaviors. The Stop Signal Task (SST) (Logan, 1994) is a well-validated measure of response inhibition that has been used in previous studies and obesity (Mole, 2015; Svaldi, 2014). Participants respond to left and right-facing arrows (go signal) on the computer screen. On 25% of trials of the 64-trial task blocks, a stop signal (an 800-Hz, 100-ms, 70-dB tone) is presented indicating that response should be inhibited. The initial stop delay in each block is 250ms and adjusts ±50ms depending on whether the participant successfully inhibits (Logan, 1994). The primary outcome is stop signal reaction time (SSRT), calculated as the mean RT on go-trials minus mean stop delay. The Stroop Test is a well-validated measure of interference control, or the ability to suppress habitual responses when shown a colored word and being asked to press the key associated with the color of the word rather than the word itself (Stroop 1935). Higher interference scores are associated with obesity (Cohen, 2011; Fagundo, 2012)

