**Frequently-Sampled Intravenous Glucose Tolerance (FSIGT) Test.** The FSIGT will occur in the CHPS on the second morning at 0800h (with glucose injection) after an 11h overnight fast (participants will stop eating by 2100h the night before). Following baseline blood sampling of 4mL at -15, -10 and -5 minutes, 0.3 g/kg of 50% glucose will be injected over 1 min starting at t=0 and 0.03 U/kg of insulin (1 U/1 ml solution) will be injected over 30 sec starting at t = 20 min. Additional 4mL blood samples will be collected at t=2, 3, 4, 5, 6, 8, 10, 12, 14, 16, 18, 20, 22, 25, 30, 40, 50, 70, 100, 140, and 180 min after the injection of glucose (123,148). Plasma glucose will be determined in duplicate by the glucose oxidase method using an automated glucose analyzer (Hitachi 912i; Roche Diagnostic Systems). Plasma insulin will be measured in duplicate by double-antibody radioimmunoassays (Millipore, Billerica, MA) at the Penn Diabetes Research Center Radioimmunoassay & Biomarkers Core. Free fatty acids (FFA) will be measured in duplicate using enzymatic colorimetrics (Wako Chemicals, Richmond, VA). Each participants samples from all 4 FSIGT tests will be assayed simultaneously. The FSIGT parameters, acute insulin response to glucose (AIRglu), insulin sensitivity (SI), glucose effectiveness (SG), and disposition index (DI), will be derived from Bergmans minimal model using MINMOD Millennium software (version 6.02; 149). AIRglu, a measure of first-phase insulin secretion, is calculated as the incremental area under the curve (AUC) for insulin between 0 and 10 min after injection of glucose. SI, a measure of the capacity of insulin to promote glucose disposal, is modeled from the relationship of incremental insulin values over baseline to glucose disappearance. SG, a measure of the capacity of glucose to mediate its own disposal, is modeled from the effect of basal insulin levels on glucose kinetics. DI is a composite measure of -cell function that accounts for the relationship between insulin secretion and sensitivity by the product of AIRglu and SI, providing an assessment of the appropriateness of -cell compensation for changes in insulin sensitivity. The FFA profile during the FSIGT will be analyzed according to the model of Sumner et al. (150), in which 3 phases of FFA dynamics have been described during the 180 min after the injection of glucose; an extension of basal levels until the initial sustained decrease in FFA; the suppression of FFA until nadir evaluated by the fractional disposal rate; and the time from nadir to return to basal levels as also reported by our group (123). **Transcriptomics of Blood and AT.** The Wistar Institute Genomics Facility will process blood and AT for transcriptomics using standard protocols in place. Total RNA will be isolated from whole blood collected in PAXgene Blood RNA tubes (see section C.6b.) using PAXgene Blood miRNA kits (Qiagen), and Total RNA will be isolated from AT using Direct-zol RNA Miniprep kits (Zymo Research). Extracted RNA will undergo extensive quality control with the Agilent Bioanalyzer 2100 (Agilent), and Qubit fluorometric quantitation (Life Technologies) will be used to obtain accurate RNA concentrations before library preparation. QuantSeq 3mRNA-Seq Library Preparation Kits (Lexogen) will be used for library construction and KAPA Library Quantification Kits will be used for qPCR-based quantification of libraries. Library quality control will be performed with the Agilent Technology 2100 Bioanalyzer using a High Sensitivity DNA chip. Libraries will be pooled and then undergo high-throughput sequencing using the Illumina NextSeq 500.

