
amplitude and phase of expression data will use linear mixed effects cosinor analysis (154), which accounts for systematic inter-individual differences. We will fit separate linear mixed effect models for ghrelin and leptin phases as described above. For transcriptomics, gene expression count data will be normalized in R using the TMM function in edgeR (155) and voom in the limma package (156). We will use linear mixed effect models against RNA-seq depth count data to test the differences in genes between the daytime and delayed conditions. Mixed model analysis will be done on the normalized RNA count data to adjust for effects such as condition order and random subject effects using the lme4 package (157) in the R statistical environment version R-3.2.3. P-values for each test will be generated from the lmer results using the Anova function in the R car package (158). Coefficients of the lme analyses will represent the log2 fold change between the two conditions tested (change in daytime vs. change in delayed). We will use a p-value cutoff adjusted by false discovery rate of 0.05 to detect all RNA changes of statistical significance comprehensively. Pathway analysis will be run in various functional enrichment analysis tools, e.g., Metacore (Thomson Reuters) and Ingenuity Pathway Analysis software (Qiagen). We also will cluster genes by phase for each of the 4h sample bins and compare them with circadian rhythm hormone phase profiles using correlational analysis to identify how different blood markers are related as a function of eating condition; this may allow for identification of additional genes implicated in timed eating. Each phase cluster can also be analyzed for statistical significance of enrichment against a number of biological pathways and gene sets. Specific Aim 3. The goal of this aim is to compare the daytime vs. delayed eating schedule on insulin sensitivity and free fatty acid dynamics and on AT gene expression. Changes in insulin sensitivity and free fatty acid dynamics by condition will be compared with linear mixed-effects models. Statistical analysis of gene expression data will be conducted as described for Specific Aim 2. As AT and blood will be collected on the same day, we will also compare pre-post changes in AT and blood expression using meta-analyses, to identify how different tissues relate to each other as a function of eating condition. This will also allow indirect comparison of hormonal data with AT gene expression. Finally, we will correlate AT gene expression with fasting lipid and glucose levels.

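### Blood gene-expression results come from unfractionated whole blood with no planned allowance for white-cell mix, so a shift in cell share that differs by condition could be misread as within-cell regulation

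*Combined protocol and SAP*

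**What the plan says.** The specimen is whole blood. Under Procedures (Blood Draws for Transcriptomics), "2.5ml whole blood samples also will be collected every 4h" over 24 hours at each inpatient assessment. Under Transcriptomics of Blood and AT, "Total RNA will be isolated from whole blood collected in PAXgene Blood RNA tubes". No cell separation is described.

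In the Analysis Plan (Specific Aim 2), "gene expression count data will be normalized in R using the TMM function in edgeR", followed by voom. A mixed model is then fitted "to adjust for effects such as condition order and random subject effects". On interpretation, the plan states that "Coefficients of the lme analyses will represent the log2 fold change between the two conditions tested", meaning the change under daytime eating against the change under delayed eating. Genes are selected at a false discovery rate of 0.05. They go on to pathway analysis, clustering by phase against hormone phase and, under Specific Aim 3, comparison with adipose tissue.

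A complete blood count appears at screening: "They will have initial labs drawn, including a metabolic panel (including fasting glucose), lipid panel, CBC, and HbA1c". No differential is mentioned. The blood tests listed for the assessment visits include no count: "Fasting levels of glucose, insulin, adiponectin, cholesterol, triglycerides, non-esterified fatty acids (NEFAs) and CRP will be measured at 0800h".

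The documents do not mention a cell-fraction covariate, expression-based deconvolution or a cell-mix sensitivity analysis. Background sections A.4a and A.4b present altered genes as clock-gene responses, biomarkers and possible targets.

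**The concern.** In whole blood, a transcript's level is the sum over cell types of cell share times expression per cell. TMM and voom act at library level (scaling and precision weights) and do not separate these two parts. The order term and the random subject effect do not separate them either. If one schedule moves the lymphocyte share relative to the other, genes specific to lymphocytes move with it although no cell has changed its expression. The same holds for the cosinor analysis if the 24-h phase of the cell counts moves differently under the two schedules.

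At stake is what Aim 2 can conclude. Blood transcriptomics is a named secondary outcome. A coherent set of genes that follows cell share could be taken for a transcriptional mechanism and carried into the pathway, phase-cluster and adipose-blood comparisons.

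**Working it through.** **The plan's figure.** Accrual assumes 40 enrolled and 90% retention: 40 × 0.90 = 36, as stated. No effect size, SD or power is given for gene expression, so every input below except n = 36 is an assumption.

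**Fold change from mix alone.** Let f0 and f1 be the lymphocyte share in the two states, and r the ratio of lymphocyte expression to expression in other cells. Then log2 fold change = log2[(f1·r + 1 − f1)/(f0·r + 1 − f0)]. With f0 = 0.30:

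| Rise in share | r = 10 | Lymphocyte-only gene |
|---|---|---|
| 2 points | log2(3.88/3.70) = 0.069 | log2(32/30) = 0.093 |
| 3 points | log2(3.97/3.70) = 0.102 | log2(33/30) = 0.138 |
| 5 points | log2(4.15/3.70) = 0.166 | log2(35/30) = 0.222 |

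For a fall, a lymphocyte-only gene moves by log2(27/30) = −0.152 or log2(25/30) = −0.263.

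**Range for the SD.** With independent errors of SD s per sample, the difference of two pre-post changes has SD 2s at one draw time, and 2s/√7 when averaged over seven draws. For s = 0.2 these are 0.40 and 0.15; for s = 0.4 they are 0.80 and 0.30.

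**One gene.** With SD 0.4 the standard error is 0.4/√36 = 0.067. The two falls give 0.152/0.067 = 2.3 and 0.263/0.067 = 3.9. The first is a nominal p of about 0.03, which is not FDR significance across thousands of genes. With r = 10 and SD 0.3, a 5-point shift has paired-test power 0.90 at alpha 0.05 and 0.41 at 0.001; a 2-point shift has 0.27 and 0.02.

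**Many genes.** The simulation used 12,000 genes with none regulated: 10% lymphocyte-enriched and 10% depleted (3- to 15-fold), a between-person SD of the shift of 5 points, n = 36, independent residuals and Benjamini-Hochberg at 0.05. Mean hits, by residual SD of the paired contrast:

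| Mean shift | 0.1 | 0.15 | 0.2 | 0.3 | 0.5 |
|---|---|---|---|---|---|
| 1 point | 0 | 2 | 0 | 0 | 0 |
| 2 points | 29 | 7 | 3 | 0 | 0 |
| 3 points | 683 | 210 | 46 | 21 | 0 |
| 5 points | 2,254 | 1,756 | 857 | 294 | 10 |
| 7 points | 2,492 | 2,356 | 2,020 | 1,086 | 146 |

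At 3 points the medians are only 112, 10, 1, 0 and 0, so the means are driven by a few runs.

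At SD 0.4 the same set-up gave a mean of 6 hits (median 0) at 3 points and about 134 at 5 points. A repeat at 5 points gave means of 84 for a rise and 247 for a fall. If instead 5% to 10% of genes are strictly lymphocyte-only, SD 0.4 gives a median of about 360 to 810 hits for a fall to 25%, and 0 to 5 for a fall to 27%. At 10% lymphocyte-only genes, the mean at 3 points is about 85.

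With each person's change in share as a covariate, assumed free of error, mean hits fall to about 0 to 0.1 in every scenario in the table.

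**The case against.** The opposing case is strong on several points, and most of it stands.

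- **The covariate list is open.** A reader might infer that the gene model adjusts for order and participant and nothing else. The wording introduces those two as examples, and General Approach admits other prognostic covariates. An adjustment for cell mix is therefore permitted, but it is not named. A choice made after the gene list is seen protects less than a prespecified one.
- **No shift is documented.** The documents give no lymphocyte share, no shift and no gene-level SD. Assessments use the same clock times and a standardized meal schedule, diet composition and energy level are constant across conditions, and sleep timing is held fixed. These features close several routes to a shift, but do not exclude one caused by eight weeks on a schedule.
- **Common rhythms cancel.** A 24-h rhythm in cell counts shared by both conditions drops out of the between-condition contrast.
- **The hits would be real.** A reader might infer that FDR control fails. It does not for RNA abundance, which is what the coefficient measures. Telling the two states apart, or finding a biomarker, does not require attribution to a cell. Only the mechanistic and target readings do.

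**Conclusion.** The omission stands: blood fold changes and phases are to be interpreted without a planned check on white-cell mix, and no count is listed at the visits to support one. The consequence is conditional. If lymphocyte share shifted by about 5 points between conditions and the paired-contrast SD were about 0.3 to 0.4 log2 or less, roughly a hundred to several hundred or more genes could reach FDR 0.05 with none regulated. At 1 to 2 points there would be few or none. At 3 points the result turns on the SD and on how cell-specific the genes are.

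A reader might infer that any modest shift would produce a long misleading list. The documents do not support that, because they give neither a shift nor an SD. The supportable statement is that such a shift could be misread as within-cell regulation. The calculation rests on an assumed 30% baseline share, the assumed mix of cell-specific genes and independent residuals; real genes are correlated.

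**What to change.** Add a prespecified sensitivity analysis to Specific Aim 2:

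1. Estimate white-cell fractions for each blood library by expression-based deconvolution, after checking that the method suits the planned 3' mRNA-Seq data.
2. Test whether the fractions, in level and in 24-h phase, differ by eating condition.
3. Report the gene-level and cosinor results without and with the main fractions as covariates.
4. Keep the unadjusted result as the effect on RNA abundance. Where the two versions differ, qualify any claim of within-cell regulation or mechanism. Do not make survival in the adjusted model a condition for calling a gene changed.

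The reason for the last point is that cell share is observed after randomization, may itself be an effect of the schedule, and would be estimated with error from the same libraries, so adjustment can also remove real regulation.

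The cost is analysis time, with no new samples. The record shows 32 of 40 participants already enrolled, so differential counts cannot be recovered for draws already taken, whereas deconvolution uses libraries already planned. The downsides are error in the fractions (the near-zero adjusted counts above assume none) and adjustment for a variable that the schedule may affect, which is why both versions should be shown.
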